11.5 IDENTIFICATION OF SOURCE DATA

All data to be recorded on the CRF must reflect the corresponding source documents.

11.6 RETENTION OF RECORDS

The circumstances of completion or termination of the study notwithstanding, the investigator is responsible for retaining all study documents, including but not limited to the protocol, copies of CRFs, the Investigator's Brochure, and regulatory agency registration documents (eg, Form FDA 1572, ICFs, and IRB/IEC correspondence). In addition, the sponsor will send a list of treatment

codes by study subject to the investigator after the clinical database for this study has been locked. The site should plan to retain study documents, as directed by the sponsor, for at least 2 years after the last approval of a marketing application in an ICH region and until there are no pending or contemplated marketing applications in an ICH region or at least 3 years have elapsed since the formal discontinuation of clinical development of the investigational product.

It is requested that at the completion of the required retention period, or should the investigator retire or relocate, the investigator contact the sponsor, allowing the sponsor the option of permanently retaining the study records.

11.7 AUDITING PROCEDURES AND INSPECTION

In addition to the routine monitoring procedures, the sponsor's Clinical Quality Assurance department conducts audits of clinical research activities in accordance with the sponsor's SOPs to evaluate compliance with the principles of ICH GCP and all applicable local regulations. If a government regulatory authority requests an inspection during the study or after its completion, the investigator must inform the sponsor immediately.

11.8 HANDLING OF STUDY DRUG

All study drug will be supplied to the principal investigator (or a designated pharmacist) by the sponsor. Drug supplies must be kept in an appropriate secure area (eg, locked cabinet) and stored according to the conditions specified on the drug labels. The investigator (or a designated pharmacist) must maintain an accurate record of the shipment and dispensing of the study drug in a drug accountability ledger, a copy of which must be given to the sponsor at the end of the study. An accurate record of the date and amount of study drug dispensed to each subject must be available for inspection at any time. The CRA will visit the site and review these documents along with all other study conduct documents at appropriate intervals once study drug has been received by the site.

All drug supplies are to be used only for this study and not for any other purpose. The investigator (or site personnel) must not destroy any drug labels or any partly used or unused drug supply before approval to do so by the sponsor. At the conclusion of the study and as appropriate during the study, the investigator (or a designated pharmacist) will return all used and unused drug containers, drug labels, and a copy of the completed drug disposition form to the sponsor's CRA.

11.9 PUBLICATION OF RESULTS

All manuscripts, abstracts, or other modes of presentation arising from the results of the study must be reviewed and approved in writing by the sponsor in advance of submission pursuant to the terms and conditions set forth in the executed Clinical Trial Agreement between the sponsor/CRO and the institution/investigator. The review is aimed at protecting the sponsor's proprietary information existing either at the date of the commencement of the study or generated during the study.

The detailed obligations regarding the publication of any data, material results, or other information, generated or created in relation to the study shall be set out in the agreement between each investigator and the sponsor or CRO, as appropriate.

11.10 DISCLOSURE AND CONFIDENTIALITY

The contents of this protocol and any amendments and results obtained during the study should be kept confidential by the investigator, the investigator's staff, and the IRB/IEC and will not be disclosed in whole or in part to others, or used for any purpose other than reviewing or performing the study, without the written consent of the sponsor. No data collected as part of this study will be used in any written work, including publications, without the written consent of the sponsor. These obligations of confidentiality and non-use shall in no way diminish such obligations as set forth in either the Confidentiality Agreement or Clinical Trial Agreement executed between the sponsor/CRO and the institution/investigator.

All persons assisting in the performance of this study must be bound by the obligations of confidentiality and non-use set forth in either the Confidentiality Agreement or Clinical Trial Agreement executed between the institution/investigator and the sponsor/CRO.

11.11 DISCONTINUATION OF STUDY

The sponsor reserves the right to discontinue the study for medical reasons or any other reason at any time. If a study is prematurely terminated or suspended, the sponsor will promptly inform the investigators/institutions and regulatory authorities of the termination or suspension and the reason(s) for the termination or suspension. The IRB/IEC will also be informed promptly and provided the reason(s) for the termination or suspension by the sponsor or by the investigator/institution, as specified by the applicable regulatory requirement(s).

The investigator reserves the right to discontinue the study should his/her judgment so dictate. If the investigator terminates or suspends a study without prior agreement of the sponsor, the investigator should inform the institution where applicable, and the investigator/institution should promptly inform the sponsor and the IRB/IEC and provide the sponsor and the IRB/IEC with a detailed written explanation of the termination or suspension. Study records must be retained as noted above.

11.12 SUBJECT INSURANCE AND INDEMNITY

The sponsor will provide insurance for any subjects participating in the study in accordance with all applicable laws and regulations.

12 APPENDICES

Appendix 1 Sponsor's Grading for Laboratory Values

(revised per Amendment 02)

Sponsor's Grading for Laboratory Values				
	Grade 1	Grade 2	Grade 3	Grade 4
BLOOD/BONE MARROW				
Hemoglobin	< LLN – 10.0 g/dL < LLN – 100 g/L < LLN – 6.2 mmol/L	< 10.0 – 8.0 g/dL < 100 – 80 g/L < 6.2 – 4.9 mmol/L	< 8.0 g/dL < 80 g/L < 4.9 mmol/L; transfusion indicated	life-threatening consequences; urgent intervention indicated
Leukocytes (total WBC)	< LLN – 3.0 x 10 ⁹ /L < LLN – 3000/mm ³	< 3.0 – 2.0 x 10 ⁹ /L < 3000 – 2000/mm ³	< 2.0 – 1.0 x 10 ⁹ /L < 2000 – 1000/mm ³	< 1.0 x 10 ⁹ /L < 1000/mm ³
Lymphocytes	< LLN – 800/mm ³ < LLN – 0.8 x 10 ⁹ /L	< 800 – 500/mm ³ < 0.8 – 0.5 x 10 ⁹ /L	< 500 – 200/mm ³ < 0.5 – 0.2 x 10 ⁹ /L	< 200/mm ³ < 0.2 x 10 ⁹ /L
Neutrophils	< LLN – 1.5 x 10 ⁹ /L < LLN – 1500/mm ³	< 1.5 – 1.0 x 10 ⁹ /L < 1500 – 1000/mm ³	< 1.0 – 0.5 x 10 ⁹ /L < 1000 – 500/mm ³	< 0.5 x 10 ⁹ /L < 500/mm ³
Platelets	< LLN – 75.0 x 10 ⁹ /L < LLN – 75,000/mm ³	< 75.0 – 50.0 x 10 ⁹ /L < 75,000 – 50,000/mm ³	< 50.0 – 25.0 x 10 ⁹ /L < 50,000 – 25,000/mm ³	< 25.0 x 10 ⁹ /L < 25,000/mm ³
METABOLIC/LABORATORY				
Albumin, serum- low (hypoalbuminemia)	< LLN – 3 g/dL < LLN – 30 g/L	< 3 – 2 g/dL < 30 – 20 g/L	< 2 g/dL < 20 g/L	life-threatening consequences; urgent intervention indicated
Alkaline phosphatase	> ULN – 3.0 x ULN	> 3.0 – 5.0 x ULN	> 5.0 – 20.0 x ULN	> 20.0 x ULN
ALT	> ULN – 3.0 x ULN	> 3.0 – 5.0 x ULN	> 5.0 – 20.0 x ULN	> 20.0 x ULN
AST	> ULN – 3.0 x ULN	> 3.0 – 5.0 x ULN	> 5.0 – 20.0 x ULN	> 20.0 x ULN
Bicarbonate, serum-low	< LLN – 16 mmol/L	< 16 – 11 mmol/L	< 11 – 8 mmol/L	< 8 mmol/L
Bilirubin (hyperbilirubinemia)	> ULN – 1.5 x ULN	> 1.5 – 3.0 x ULN	> 3.0 – 10.0 x ULN	> 10.0 x ULN
Calcium, serum-low (hypocalcemia)	< LLN – 8.0 mg/dL < LLN – 2.0 mmol/L	< 8.0 – 7.0 mg/dL < 2.0 – 1.75 mmol/L	< 7.0 – 6.0 mg/dL < 1.75 – 1.5 mmol/L	< 6.0 mg/dL < 1.5 mmol/L
Calcium, serum-high (hypercalcemia)	> ULN – 11.5 mg/dL > ULN – 2.9 mmol/L	> 11.5 – 12.5 mg/dL > 2.9 – 3.1 mmol/L	> 12.5 – 13.5 mg/dL > 3.1 – 3.4 mmol/L	> 13.5 mg/dL > 3.4 mmol/L
Cholesterol, serum-high (hypercholesterolemia)	> ULN – 300 mg/dL > ULN – 7.75 mmol/L	> 300 – 400 mg/dL > 7.75 – 10.34 mmol/L	> 400 – 500 mg/dL > 10.34 – 12.92 mmol/L	> 500 mg/dL > 12.92 mmol/L
Creatinine	> ULN – 1.5 x ULN	> 1.5 – 3.0 x ULN	> 3.0 – 6.0 x ULN	> 6.0 x ULN
GGT (γ-Glutamyl transpeptidase)	> ULN – 3.0 x ULN	> 3.0 – 5.0 x ULN	> 5.0 – 20.0 x ULN	> 20.0 x ULN
Glucose, serum-high (hyperglycemia)	Fasting glucose value: > ULN – 160 mg/dL > ULN – 8.9 mmol/L	Fasting glucose value: > 160 – 250 mg/dL > 8.9 – 13.9 mmol/L	Fasting glucose value: > 250 – 500 mg/dL; > 13.9 – 27.8 mmol/L; hospitalization indicated	Fasting glucose value: > 500 mg/dL; > 27.8 mmol/L; life-threatening consequences
Glucose, serum-low (hypoglycemia)	< LLN – 55 mg/dL < LLN – 3.0 mmol/L	< 55 – 40 mg/dL < 3.0 – 2.2 mmol/L	< 40 – 30 mg/dL < 2.2 – 1.7 mmol/L	< 30 mg/dL < 1.7 mmol/L life-threatening consequences; seizures
Phosphate, serum-low (hypophosphatemia)	< LLN – 2.5 mg/dL < LLN – 0.8 mmol/L	< 2.5 – 2.0 mg/dL < 0.8 – 0.6 mmol/L	< 2.0 – 1.0 mg/dL < 0.6 – 0.3 mmol/L	< 1.0 mg/dL < 0.3 mmol/L life-threatening consequences
Potassium, serum-high (hyperkalemia)	> ULN – 5.5 mmol/L	> 5.5 – 6.0 mmol/L	> 6.0 – 7.0 mmol/L hospitalization indicated	> 7.0 mmol/L life-threatening consequences
Potassium, serum-low (hypokalemia)	< LLN – 3.0 mmol/L	< LLN – 3.0 mmol/L; symptomatic; intervention indicated	< 3.0 – 2.5 mmol/L hospitalization indicated	< 2.5 mmol/L life-threatening consequences

Sponsor's Grading for Laboratory Values				
	Grade 1	Grade 2	Grade 3	Grade 4
Sodium, serum-high (hypernatremia)	> ULN – 150 mmol/L	> 150 – 155 mmol/L	> 155 – 160 mmol/L hospitalization indicated	> 160 mmol/L life-threatening consequences
Sodium, serum-low (hyponatremia)	< LLN – 130 mmol/L	N/A	< 130 – 120 mmol/L	< 120 mmol/L life-threatening consequences
Triglyceride, serum-high (hypertriglyceridemia)	150 – 300 mg/dL 1.71 – 3.42 mmol/L	> 300 – 500 mg/dL > 3.42 – 5.7 mmol/L	> 500 – 1000 mg/dL >5.7 – 11.4 mmol/L	> 1000 mg/dL > 11.4 mmol/L life-threatening consequences
Uric acid, serum-high (hyperuricemia)	> ULN – 10 mg/dL ≤ 0.59 mmol/L without physiologic consequences	N/A	> ULN – 10 mg/dL ≤ 0.59 mmol/L with physiologic consequences	> 10 mg/dL > 0.59 mmol/L life-threatening consequences

ALT = alanine aminotransferase (serum glutamic pyruvic transaminase), AST = aspartate aminotransferase (serum glutamic oxaloacetic transaminase), GGT = γ -glutamyl transpeptidase, N/A = not applicable, LLN = lower limit of normal, ULN = upper limit of normal, WBC = white blood cell.

Based on Common Terminology Criteria for Adverse events (CTCAE) Version 4.0. Published: May 28, 2009 (v4.03: June 14, 2010).

Appendix 2 List of P-glycoprotein Inhibitors

Inhibitor	Therapeutic Class
amiodarone	Antiarrhythmics
azithromycin	Antibiotics
captopril	ACE Inhibitors
carvedilol	α/β Adrenergic Antagonists
clarithromycin	Antibiotics
conivaptan	Diuretics
cremophor	RH40 Transporter Modulators
cyclosporine	Immunosuppressive
diltiazem	Calcium Channel Blockers
dronedarone	Antiarrhythmics
elacridar (GF120918)	Transporter Modulators
erythromycin	Antibiotics
felodipine	Calcium Channel Blockers
ginkgo	Herbal Medications
indinavir and ritonavir	Protease Inhibitors
itraconazole	Antifungals
ketoconazole	Antifungal
lopinavir and ritonavir	Protease Inhibitors
mibefradil	Calcium Channel Blockers
milk thistle	Herbal Medications
nifedipine	Calcium Channel Blockers
nitrendipine	Calcium Channel Blockers
quinidine	Antiarrhythmics
ranolazine	Cardiovascular Drugs
ritonavir	Protease Inhibitors
talinolol	α/β Adrenergic Antagonists
telaprevir	Antivirals
telmisartan	Angiotensin II Inhibitors
tipranavir/ritonavir	Protease Inhibitors
tolvaptan	Vasopressin Antagonist
valsopodar (PSC 833)	Transporter Modulators
verapamil	Calcium Channel Blockers

Source: University of Washington Drug Drug Interaction database (except for cyclosporine and ketoconazole)

Appendix 3 Guidelines for Doppler Sonography Measurements

The key to collecting relevant ultrasound data is consistency. The following measures are adopted to minimize the variability of data obtained.

Minimize subject variability:

- The subject should be fasting for at least 4 hours prior to the Doppler sonography
 - *Rationale: Portal vein flow rate increases after food intake*
- The subject should be in the supine position for at least 15 minutes prior to the Doppler sonography
 - *Rationale: Posture has an impact on portal vein flow rate. Standardizing posture across study sites can minimize variability*
- The subject should be instructed to take a full inspiration and hold his/her breath for a few seconds during portal vein flow measurement
 - *Rationale: Measuring portal vein flow rate at the same point in the respiratory cycle can minimize variability*

Minimize operator variability:

In order to minimize operator variability, the following instructions are provided:

- When possible, the same trained sonography operator will perform all of the Doppler sonography testing on all subjects at the study site throughout the study.
- The portal vein should be scanned longitudinally
- Sample volume should be positioned in the center of the vessel, in the tract underneath the hepatic artery, covering 50% of the vessel diameter
- The Doppler angle should be 55° or just below
- Pulse repetition frequency should be 4 kHz; the high pass filter should be adjusted to 100 Hz
- The Doppler and B-mode tracings should be recorded simultaneously
- The average portal blood maximum velocity should be obtained by manual tracing of the upper limit of the Doppler waveforms
- The Doppler waveform calculation should be obtained by covering 2 cardiac cycles between 3 arterial wall artifacts

- Portal vein diameter should be measured from the inner anterior to the inner posterior wall

Three main portal vein blood flow velocity measurements, lasting no less than 4 seconds, will be recorded, and the mean of the 3 values recorded as the final reading.

Minimize equipment variability:

Different equipment may furnish different results due to interequipment variability. Therefore, the sponsor recommends that the same Doppler equipment should be used at the study site throughout the study.

PROTOCOL SIGNATURE PAGE

Study Protocol Number: E5501-G000-311

**16.1.9            Documentation of Statistical Methods**

The final approved Statistical Analysis Plan and other statistical documents, as applicable, for this study are provided in the [following pages](#).

**2 LIST OF ABBREVIATIONS AND DEFINITIONS OF TERMS**

Abbreviation	Term
AE	adverse event
ANOVA	analysis of variance
ATC	anatomical therapeutic class
BARC	Bleeding Academic Research Consortium
BCLC	Barcelona-Clinic Liver Cancer
BMI	body mass index
CI	confidence interval
CMH	Cochran-Mantel-Haenszel
CRF	case report form
CTCAE	common terminology criteria for adverse events
CTP	Child-Turcotte-Pugh
DSMB	data safety monitoring board
ECG	electrocardiogram
FAS	full analysis set
HCC	hepatocellular carcinoma
LNH	low/normal/high
INR	international normalized ratio
MedDRA	Medical Dictionary for Regulatory Activities
MELD	Model for End-stage Liver Disease
NI	non-inferiority
PD	pharmacodynamic
PK	pharmacokinetic
PP	per protocol analysis set
PT	preferred term
QTcB	corrected QT interval by Bazett's formula
QTcF	corrected QT interval by Fridericia's formula
SAE	serious adverse event
SAP	statistical analysis plan
SD	standard deviation
SI	Système International
SMQ	Standardized MedDRA Query
SOC	System Organ Class
TEAE	treatment-emergent adverse event
TEMAV	treatment-emergent markedly abnormal laboratory values
TLG	tables, listings, and graphs
WHO	World Health Organization
WHO DD	World Health Organization Drug Dictionary

### 3 INTRODUCTION

The purpose of this statistical analysis plan (SAP) is to describe the procedures and the statistical methods that will be used to analyze and report results for Eisai Protocol E5501-G000-311 (Version 7.0), Amendment 4.

This document is prepared based on the study protocol (dated December 2, 2016). Reader is referred to the final study protocol, the case report form (CRF), general CRF completion guidelines for details of study design, conduct and data collection.

#### 3.1 STUDY OBJECTIVES

##### 3.1.1 Primary Objective(s)

The primary objective of the study is to confirm that avatrombopag (60 mg avatrombopag for subjects with platelet count  $<40 \times 10^9/L$  and 40 mg avatrombopag for subjects with platelet count from 40 to  $<50 \times 10^9/L$ ) is superior to placebo in removing the need for platelet transfusions or any rescue procedure for bleeding after randomization and up to 7 days following an elective procedure in chronic liver disease patients who have thrombocytopenia.

##### 3.1.2 Secondary Objective(s)

The secondary objectives of the study are:

- To confirm that avatrombopag is superior to placebo in achieving a platelet count of  $\geq 50 \times 10^9/L$  on Procedure Day in the proposed target population
- To confirm that avatrombopag is superior to placebo in elevating platelet counts from baseline on Procedure Day in the proposed target population
- To evaluate the safety of avatrombopag in the proposed target population

##### 3.1.3 Exploratory Objective(s)

The exploratory objectives of the study are:

- To characterize the pharmacokinetics (PK) and the relationship between avatrombopag plasma concentrations and platelet count using the population approach
- To characterize platelet count changes from baseline, the extent of platelet transfusion use, evaluate the incidence of bleeding events, and assess the severity of any bleeding events
- To evaluate the health economic impact associated with minimizing the need for platelet transfusions and any rescue procedure for bleeding associated with an elective procedure

### 3.2 OVERALL STUDY DESIGN AND PLAN

E5501-G000-311 is a Phase 3, global, multicenter, randomized, double-blind, placebo-controlled, parallel group study using avatrombopag to treat adults with thrombocytopenia associated with liver disease prior to an elective procedure.

Subjects meeting all entry criteria will be enrolled into 2 cohorts according to mean baseline platelet count ( $<40 \times 10^9/L$  or from 40 to  $<50 \times 10^9/L$ ). Within each cohort, subjects will be further stratified by the risk of bleeding associated with the elective procedure (low, moderate or high) and hepatocellular carcinoma (HCC) status (Yes or No). From previous studies, it is anticipated that the 2 baseline platelet count cohorts ( $<40 \times 10^9/L$  and from 40 to  $<50 \times 10^9/L$ ) will be equally represented. However, neither baseline platelet count cohort will be permitted to comprise greater than 55% of the total number of subjects enrolled into the study.

Permitted procedures and the risk of bleeding associated with each procedure are listed in [Table 1](#). It is planned that no fewer than 10% of subjects will be enrolled into the high risk group and no more than 60% of subjects in the low-risk group.

**Table 1 Permitted Procedures and the Risk of Bleeding Associated with Each Procedure**

Risk of Bleeding Associated with Procedure	Procedure
Low risk	Paracentesis
	Thoracentesis
	Gastrointestinal endoscopy with or without plans for biopsy, colonoscopy, polypectomy, or variceal banding
Moderate risk	Liver biopsy
	Bronchoscopy with or without plans for biopsy
	Ethanol ablation therapy or chemoembolization for HCC
High risk	Vascular catheterization (including right side procedures in subjects with pulmonary hypertension)
	Transjugular intrahepatic portosystemic shunt
	Dental procedures
	Renal biopsy
	Biliary interventions
	Nephrostomy tube placement
	Radiofrequency ablation
Laparoscopic interventions	

Level of risk based on key opinion leader (KOL) input and [Malloy PC](#), Grassi CJ, Kundu S, Gervais DA, Miller DL, Osnis RB, et al. for the Standards of Practice Committee with Cardiovascular and Interventional Radiological Society of Europe (CIRSE) Endorsement. Consensus guidelines for periprocedural management of coagulation status and hemostasis risk in percutaneous image-guided interventions. *J Vasc Interv Radiol* 2009; 20:S240–9.

Within the **lower** baseline platelet count cohort ( $<40 \times 10^9/L$ ) and each stratum, subjects will be randomized in a 2:1 ratio to receive avatrombopag or matching placebo as follows:

- 60 mg avatrombopag on Days 1 to 5 (Group A)
- Matching placebo on Days 1 to 5 (Group B)

Within the **higher** baseline platelet count cohort (from 40 to  $<50 \times 10^9/L$ ) and each stratum, subjects will be randomized in a 2:1 ratio to receive avatrombopag or matching placebo as follows:

- 40 mg avatrombopag on Days 1 to 5 (Group C)
- Matching placebo on Days 1 to 5 (Group D)

Platelet counts must be measured on 2 separate occasions, during the Screening Period and at Baseline, and must be performed at least one day apart with neither platelet count  $>60 \times 10^9/L$ . The average of these 2 platelet counts will be used for entry criteria (the mean baseline platelet count of  $<50 \times 10^9/L$ ). The elective surgical or diagnostic procedure is scheduled to be performed within 10 to 13 days of first dose of study drug.

This study will consist of 3 phases: Prerandomization, Randomization, and Follow-up Phases.

The Prerandomization Phase consists of a Screening Period (Visit 1) that will take place from Day -14 through Day -1. During this period, the type and schedule of the elective procedure will be confirmed.

The Randomization Phase includes the Baseline Period, Treatment Period, and Procedure Day. During the Baseline Period (Visit 2), subjects who have met all entry criteria, provided signed informed consent, and been randomized will be instructed to take study drug during the Treatment Period on Days 1 to 5. During the Treatment Period, subjects will come in for PK samplings on Day 4 (Visit 3). The elective procedure will be performed 5 to 8 days after last dose of study drug (Study Day 10 to 13) after all assessments on Visit 4 (Procedure Day) have been performed. The elective procedure for those subjects whose preprocedural platelet count is  $>200 \times 10^9/L$  on Visit 4 may be delayed at the discretion of the investigator until platelet counts are below  $200 \times 10^9/L$ . All subjects whose platelet count exceeds  $200 \times 10^9/L$  will be required to have a Doppler assessment at Visit 5.

The Follow-up Phase encompasses 2 visits: 7 days post Procedure Day (Visit 5) and 30 days after receiving the last dose of study drug (Visit 6).

An overview of the study design is presented in [Figure 1](#)

[figure not shown]

Figure 1 Study Design

PLT = platelet count; R = randomization

Platelet counts must be measured on 2 separate occasions, during the Screening Period and at Baseline, and must be performed at least one day apart with neither platelet count  $>60 \times 10^9/L$ . The mean of these 2 platelet counts (mean baseline platelet count  $<50 \times 10^9/L$ ) will be used for entry criteria and determination of baseline platelet count.

a: Visit 3 occurs on Day 4 ( $\pm 1$  day) during the Treatment Period.

#### 4 DETERMINATION OF SAMPLE SIZE

The proposed sample size was based on comparisons of the primary efficacy variable, with the response rate defined as the proportion of subjects who do not require a platelet transfusion or any rescue procedure for bleeding after randomization and up to 7 days following an elective procedure. Based on clinical opinion and the published results of a similar compound in adults with thrombocytopenia associated with liver disease (ELtrombopag EVALuated for its Ability to overcome Thrombocytopenia and Enable procedures [ELEVATE] study [Afdahl, 2012]), the response rate in the placebo group is assumed to be 18%. Within each baseline platelet count cohort, a sample size of 100 randomized subjects, 67 subjects for avatrombopag and 33 subjects for placebo, would have greater than 90% power to detect an absolute difference of 35% between the avatrombopag response rate and the placebo response rate assuming 18% response rate for placebo using Fisher's Exact tests with a 2-sided  $\alpha=0.05$ . The hypothesized treatment group difference was based on platelet count changes found in the Phase 2 study (E5501-G000-202) and dose-response modeling using data from that study and others in the project development. Based on the baseline data in the Phase 2 study and assuming these were projected to be similar for this study, it was anticipated that this study would enroll roughly half of the total number of subjects in each of the 2 baseline platelet count cohorts to make the total sample size of 200 randomized subjects, 133 subjects for avatrombopag and 67 subjects for placebo.

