16.1.1 Protocol and Protocol Amendments

The [final study protocol](#) is provided on the following pages.

Revisions to V6.0: 31 May 2016 (Amendment 03) Date: V7.0: 02 Dec 2016 (Amendment 04)		
Change	Rationale	Affected Protocol Sections
Sample size reduced from approximately 300 subjects to approximately 200 subjects	After consultation with the FDA, it was decided that the current study has reached adequate enrollment to demonstrate the safety and benefit of avatrombopag in reducing the need for platelet transfusion in subjects with thrombocytopenia and liver disease undergoing an elective procedure.	Synopsis – 
 • Number of Subjects • Sample Size Rationale Section 9.3 Section 9.4.3 Section 9.7.2
The secondary endpoint, proportion of subjects with a World Health Organization (WHO) bleeding score ≥ 2 after randomization and up to 7 days following an elective procedure, will be an exploratory endpoint	Given the rare occurrence of bleeding events (less than expected), this endpoint is better suited as an exploratory endpoint.	Synopsis – 
 • Secondary Objectives • Exploratory Objectives • Secondary Endpoints • Exploratory Endpoints • Secondary Efficacy Variable Analyses • Exploratory Efficacy Variables Section 8.2 Section 8.3 Section 9.7.1.1 Section 9.7.1.6

Revisions to V5.0: 22 June 2015 (Amendment 02) Date: V6.0: 31 May 2016 (Amendment 03)		
Change	Rationale	Affected Protocol Sections
Clarification to Inclusion Criteria #3: replace the word "change" with the word "increase"	Per FDA request	Synopsis – 
• Inclusion Criteria Section 9.3.1

REVISION HISTORY

Revisions to V4.0: 12 Nov 2013 (Amendment 01) Date: V5.0: 22 June 2015 (Amendment 02)		
Change	Rationale	Affected Protocol Sections
Revised the risk of bleeding associated with procedures	Additional procedures included in the source article (Malloy et al., 2009) that originated the initial classification were added. Ongoing study observations, supported by key opinion leader (KOL) review and current literature review resulted in additional updates in the bleeding risk categories classification	Synopsis – 
 • Study Design • Statistical Methods • Efficacy Analyses Section 9.1.2.3 
 • Table 1 Section 9.7.1.6

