9.7.2 Determination of Sample Size

The proposed sample size is based on comparisons of the primary efficacy variable, with the response rate defined as the proportion of subjects who do not require a platelet transfusion or any rescue procedure for bleeding after randomization and up to 7 days following an elective procedure. Based on clinical opinion and the published results of a similar compound in adults with thrombocytopenia associated with liver disease (ELEVATE study),¹⁰ the response rate in the placebo group is assumed to be 18%. With each baseline platelet count cohort, a sample size of 100 randomized subjects, 67 subjects for avatrombopag and 33 subjects for placebo, will have greater than 90% power to detect an absolute difference of 35% between the avatrombopag response rate and the placebo response rate assuming 18% response rate for placebo using Fisher's Exact tests with a 2-sided $\alpha=0.05$. (revised per Amendment 04) The hypothesized treatment group difference is based on platelet count changes found in the Phase 2 study (E5501-G000-202) and dose-response modeling using data from that study and others in the project development. Based on the baseline data in the Phase 2 study and assuming these are projected to be similar for this study, it is anticipated that this study will enroll roughly half of the total number of subjects in each of the 2 baseline platelet count cohorts to make the total sample size of 200 randomized subjects, 133 subjects for avatrombopag and 67 subjects for placebo. (revised per Amendment 04)

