### 5.3.3 Multiple Comparisons/Multiplicity

The primary efficacy endpoint will be tested between the individual avatrombopag treatment group (40 or 60 mg) and matching placebo within each baseline platelet count cohort ( $<40 \times 10^9/L$  or from 40 to  $<50 \times 10^9/L$ ), each at a significance level of  $\alpha=0.05$ . The primary efficacy endpoint is considered positive only if the tests are statistically significant for both baseline platelet count cohorts to control the family-wise Type I error rate at a significance level of  $\alpha=0.05$ .

A sequential gatekeeping testing procedure will be used for the secondary efficacy endpoints to control the family-wise Type I error rate at a significance level of  $\alpha=0.05$ . The secondary efficacy endpoints will be analyzed if the primary efficacy endpoint is statistically significant for both baseline platelet count cohorts. The first secondary efficacy endpoint is tested first within each baseline platelet count cohort, each at a significance level of  $\alpha=0.05$ . Only if the first secondary efficacy endpoint is statistically significant for both baseline platelet count cohorts, the analysis of second secondary efficacy endpoint will proceed within each baseline platelet count cohort, each at a significance level of  $\alpha=0.05$ . No alpha adjustment is planned for other efficacy endpoints.

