### 5.4.1 Primary Efficacy Analyses

The primary efficacy variable is the proportion of subjects who do not require a platelet transfusion or any rescue procedure for bleeding after randomization and up to 7 days following an elective procedure.

The null hypothesis is that the proportion of subjects not requiring a platelet transfusion or any rescue procedure for bleeding after randomization and up to 7 days following an elective procedure is the same between the avatrombopag and placebo treatment groups. The corresponding alternative hypothesis is that the proportion of subjects not requiring a platelet transfusion or any rescue procedure for bleeding after randomization and up to 7 days following an elective procedure is not the same between avatrombopag and placebo. This hypothesis will be tested separately with each baseline platelet count cohort.

The proportion of subjects not requiring a platelet transfusion or any rescue procedure for bleeding will be tested between the individual avatrombopag treatment group (40 or 60mg) and matching placebo within each baseline platelet count cohort ( $<40 \times 10^9/L$  or from 40 to  $<50 \times 10^9/L$ ), each at a significance level of  $\alpha=0.05$  using the generalized Cochran Mantel Haenszel (CMH) test adjusting for the risk of bleeding associated with the elective procedure (low, moderate, or high based on Amendment 02 categorization).

- For subjects with platelet count  $<40 \times 10^9/L$  at baseline, the treatment comparison will be carried out between the 60 mg avatrombopag treatment group (Group A) versus matching placebo (Group B).
- For subjects with platelet count from 40 to  $<50 \times 10^9/L$  at baseline, the treatment comparison will be carried out between the 40 mg avatrombopag treatment group (Group C) versus matching placebo (Group D).

This study will be considered as positive if statistical significance is achieved for primary efficacy endpoints for both baseline platelet count cohorts.

The 95% CI for the proportion of subjects not requiring a platelet transfusion or any rescue procedure for bleeding will be calculated for each treatment group within each baseline platelet count cohort. In addition, the 95% CI for the difference between avatrombopag and matching placebo will also be provided within each baseline platelet count cohort using normal approximation method.

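### Does the stated power of more than 90% need changing because the study succeeds only if both platelet-count cohorts are significant?

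*SAP*

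**What the plan says.** SAP section 4 sizes the trial one cohort at a time. Its sentence is limited at the outset to each baseline platelet count cohort, and it says that "a sample size of 100 randomized subjects, 67 subjects for avatrombopag and 33 subjects for placebo, would have greater than 90% power to detect" the planned effect. The inputs are a placebo rate ("the response rate in the placebo group is assumed to be 18" percent), "an absolute difference of 35% between the avatrombopag response rate and the placebo response rate", and a calculation "using Fisher's Exact tests with a 2-sided" alpha of 0.05. Two such cohorts make up the total of 200. Protocol section 9.7.2 and the synopsis carry the same statement: each cohort "will have greater than 90% power to detect an absolute difference of 35% between the avatrombopag response rate and the placebo response rate".

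The success rule stands elsewhere. SAP section 5.3.3 tests the two cohorts "each at a significance level of" 0.05. SAP section 5.4.1 then says: "This study will be considered as positive if statistical significance is achieved for primary efficacy endpoints for both baseline platelet count cohorts". Section 5.3.3 also opens the secondary endpoints only if both primary tests succeed.

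The Amendment 04 entry in the protocol's revision history records: "Sample size reduced from approximately 300 subjects to approximately 200 subjects". The power sentence in protocol section 9.7.2 is tagged as revised by that amendment.

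**The concern.** When success requires two tests to be significant, power for the trial is lower than power for either test. A reader who sets the figure of more than 90% beside the both-cohorts rule may take the planned risk of a failed study to be under 10%. On the sponsor's own inputs and test it is about 14%. A miss in one cohort fails the study and also closes all secondary testing, so the joint probability is the one that matters to the sponsor. The sample had also just been cut by about a third, which is when one would expect power for the real decision to be restated.

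**Working it through.** **Inputs**, all from SAP sections 3.2, 4, 5.3.3 and 5.4.1:

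- placebo response 18%; avatrombopag response 18% + 35% = 53%, the same in both cohorts
- 67 avatrombopag and 33 placebo subjects per cohort (2:1)
- two-sided alpha 0.05 in each cohort, with no split
- power computed for Fisher's exact test; the primary analysis is a CMH test stratified by bleeding risk
- neither cohort to exceed 55% of the total

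**Step 1. Reproduce the stated figure.** With X ~ Binomial(67, 0.53) and Y ~ Binomial(33, 0.18), exact power is the sum of P(X = x) × P(Y = y) over all tables (x, y) whose two-sided Fisher p-value is at most 0.05. The result is 0.9262, so the statement of more than 90% per cohort is reproduced.

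**Step 2. Power for the success rule.** The cohorts contain different subjects, so their tests are independent and

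P(both significant) = P(lower cohort significant) × P(higher cohort significant).

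By Fisher's exact test this is 0.9262 × 0.9262 = 0.858. The planned risk of missing is 1 − 0.858 = 0.142.

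**Step 3. Repeat for the test that decides the trial.** Fisher's exact test is only a sensitivity analysis (SAP section 5.4.1.1).

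| Test, 67/33 per cohort | Per cohort | Both cohorts |
|---|---|---|
| Fisher's exact | 92.6% | 85.8% |
| Mantel-Haenszel chi-square, unstratified, exact enumeration | 94.1% | 88.6% |
| CMH with three strata, simulated | about 94.2% | 88.6% to 88.7% |
| Pooled normal approximation | 94.5% | 89.3% |

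The simulation assumes 53% against 18% in every stratum and low/moderate/high mixes of 60/30/10 or 50/25/25. The documents give only limits on the mix (at most 60% low risk, at least 10% high risk), so these mixes are assumptions.

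**Step 4. Uneven cohorts.** At the permitted extreme of 110 and 90 subjects (73/37 and 60/30), Fisher power is 0.9542 × 0.9035 = 0.862. The Mantel-Haenszel version is 0.9622 × 0.9150 = 0.880. The split hardly matters.

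**Step 5. What 90% jointly would take.** By Fisher's exact test, 72/36 per cohort gives 0.9530 each and 0.9530² = 0.908 jointly. That is 108 per cohort, or 216 in all, against the planned 200 (searched in steps of 3 per cohort).

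**Two figures that rest on assumptions outside the documents:**

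- *Missing outcomes.* They count as transfused, and no dropout rate is given. If 5% were missing and the planning rates did not already allow for it, the rates become 0.95 × 53% = 50.35% and 0.95 × 18% = 17.1%. Joint power is then 82.4% (Fisher) or 85.2% (Mantel-Haenszel).
- *The earlier sample of about 300.* If it had been 100/50 per cohort with the same rates, joint Fisher power would have been 0.9905² = 98.1%. The documents do not show the earlier allocation, rates or power statement, so no firm claim about the loss of power can be built on this.

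**The case for a change.** The strongest case for a change is that a sample-size section should give the power of the decision the trial will make. This one gives the power of a component, and the text was reopened at Amendment 04 without adding the joint figure. Every variant computed above falls below 90%, and a corrective sentence would cost almost nothing.

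Much of this stands. The omission is real, the product rule is valid, and the joint figure is the more informative one.

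Three things do not stand:

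- The documents do not overstate anything. The figure is explicitly per cohort and correct as such, and no power is claimed for study success.
- The 86% figure, and the 14% risk that goes with it, belong to a test that is not primary. For the planned CMH test the risk is about 11%, and the shortfall from 90% is between 1 and 2 points.
- The claim that the amendment sharply raised the risk of failure needs an earlier design that the documents do not show.

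**Conclusion.** No change to the plan is called for. The power statement is correct for what it describes: 92.6% per cohort by Fisher's exact test, about 94% by the CMH test. What is missing is a derived figure, about 86% (Fisher) to 89% (CMH) for significance in both cohorts. It assumes 53% against 18% in each cohort, 67/33 per cohort and independent cohorts.

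A reader can obtain that figure by squaring the per-cohort power, and it is a defensible level for a confirmatory trial. The both-cohorts rule needs no split of alpha and does not inflate the type I error; its cost is in power alone. The revision history says the reduced sample was settled after consultation with the regulator, which judged enrolment adequate jointly with the sponsor's decision to stop there. Stating the joint figure would change neither how the trial is run nor how its result is read. A sponsor who wished to add it should name the test, since the Fisher figure alone understates power for the primary analysis.
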